## **1.2. Randomization**

Central randomization was implemented in this study. Subjects were randomly assigned to 1 of 2 treatment groups based on a computer-generated randomization schedule prepared by an external vendor based on the specification tested by the sponsor before the study. The randomization was balanced by using randomly permuted blocks; the randomization did not incorporate any stratification factors.

## **1.3. Trial Objectives**

### **1.3.1. Primary Objective**

In subjects with T2DM receiving standard of care but with inadequate glycemic control and at elevated risk of CV events, to assess the effect of canagliflozin compared to placebo on progression of albuminuria.

### **1.3.2. Secondary Objectives**

In subjects with T2DM receiving standard of care but with inadequate glycemic control and at elevated risk of CV events, to assess the effect of canagliflozin compared to placebo on:

- The composite endpoint of death from CV causes or hospitalization for heart failure;
- Death from CV causes.

### **1.3.3. Exploratory Objectives**

In subjects with T2DM receiving standard of care but with inadequate glycemic control and at elevated risk of CV events, to assess the effect of canagliflozin compared to placebo on:

- Regression of albuminuria;
- Change in estimated glomerular filtration rate (eGFR) from baseline to the last off-drug value;
- Urinary albumin/creatinine ratio (ACR);
- The composite of 40% decrease in eGFR, renal death or requirement for renal replacement therapy;
- The composite of doubling of serum creatinine (SCr), renal death or requirement for renal replacement therapy;
- The composite of 40% decrease in eGFR, renal death, requirement for renal replacement therapy or CV death;

- The composite of doubling of SCr, renal death, requirement for renal replacement therapy or CV death;
- The composite of 40% decrease in eGFR, conversion to macroalbuminuria, renal death or requirement for renal replacement therapy;
- The composite of doubling of SCr, conversion to macroalbuminuria, renal death or requirement for renal replacement therapy;
- Change in eGFR determined from a between-group comparison of the eGFR slopes using all on-drug measurements (ie, off-drug values will not be included) of eGFR made from the first on-drug measurement to the final on-drug measurement;
- Changes in HbA1c;
- Utilization of AHA therapy.

#### **1.4. Statistical Hypotheses**

The hypotheses in CANVAS-R are to support superiority claims of canagliflozin relative to placebo in reducing the following events:

- Progression of albuminuria;
- The composite endpoint of death from CV causes or hospitalization for heart failure;
- Death from CV causes.

For each endpoint, the following statistical hypothesis on the hazard ratio (HR) of canagliflozin over placebo will be tested:

H0: The hazard ratio  $\geq 1.0$ , versus H1: The hazard ratio  $< 1.0$

Canagliflozin will be claimed to be superior in the reduction of the target events as compared to placebo if the upper bound of 95% CIs of the hazard ratio is less than 1.0.

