11.3.4. Multiplicity Adjustment

A testing sequence for the CV program consisting of the integrated database of CANVAS and CANVAS-R is specified. The testing of the endpoints in CANVAS-R is specified as part of the sequence. To control the type I error in the CV program, testing of the hypotheses in CANVAS-R will not proceed until the hypothesis tests related to the integrated database are significant. When the hypotheses in the integrated analysis succeed in rejecting the null hypotheses, all of the alpha for testing (ie, 5%) will pass to CANVAS-R. The primary and the key secondary endpoints will be tested as follows.

Hypothesis

For other efficacy endpoints assessed in CANVAS-R, nominal p-values will be reported.

There are no interim analyses planned.

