## **4. EFFICACY**

The analysis will be performed based on the ITT analysis set, if not otherwise specified.

All statistical tests, except those for the primary and secondary efficacy endpoints, will be considered nominal and reported with a 2-sided 95% confidence level.

Unless otherwise stated, all efficacy analyses and summaries will be performed using the treatment groups assigned by IWRS.

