#### **4.1.2. Analysis Methods**

At each visit, the geometric mean of the duplicate measurements will be computed and used for all subsequent analyses unless otherwise specified. For ACR values below the lower quantifiable limit, the lower quantifiable limit itself will be used in the geometric mean calculation.

As the primary analysis for the primary efficacy endpoint, the time from Day 1 to first visit date observing progression (ie, using the visit date of the original sample collection and not using the visit date of the confirmatory sample collection) of albuminuria will be analyzed using a Cox proportional hazards regression model. The response variable in the model is time to progression and the model will include treatment and baseline albuminuria status as the explanatory variables. The hazard ratio of canagliflozin compared to placebo and its 95% CI will be estimated. Canagliflozin will be considered superior to placebo in the reduction of progression if the p-value of the test of significance, ie, the Wald test from the Cox model specified above, is  $\leq 0.05$  in the context of multiplicity adjustment described in Section 4.3.

For ITT analysis, endpoint events that occur during the data period (see Table 1) will be considered as eligible events; otherwise subjects will be censored at the last ACR measurement up to GTED.

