#### 4.2.2.1. The Composite of CV Death or Hospitalization for Heart Failure

The analysis will be based on time to the first occurrence of the composite event using ITT analysis set. The hazard ratio of canagliflozin compared to placebo and its 95% CI will be estimated using a stratified Cox proportional hazards regression model with treatment as the explanatory variable and history of CV disease (secondary and primary prevention) as the stratification factor. The p-value from the stratified log rank test for the treatment effect will also be reported.

The subgroup analysis will be conducted using the same approaches described in Section 4.1.3 and the following subgroups:

- Age group: <65, ≥65 years old;
- Sex: Male, Female;
- Race: White, Black or African American, Asian, Other;
- Region: Central/South America, Europe, North America, Rest of the World;
- Baseline BMI categories (<30, ≥30 kg/m^2);
- Baseline composite blood pressure categories ([SBP <140 or DBP <90 mmHg] vs. [SBP ≥140 and DBP ≥90 mmHg]);
- Baseline eGFR categories (30 to <60, 60 to <90, ≥90 mL/min/1.73m^2);
- Baseline HbA1c ≥ 8%: Yes/No;
- Duration of diabetes ≥ 10 years: Yes/No;
- History of CV disease: Yes/No;
- History of peripheral vascular disease: Yes/No;

---

a Undetermined death is considered CV death.

- History of amputation: Yes/No;
- Baseline use of statin;
- Baseline use of anti-thrombotics;
- Baseline use of RAAS inhibitor;
- Baseline use of Beta blocker;
- Baseline use of insulin;
- Baseline use of diuretics.

[figure not shown]

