#### **4.2.2.2. CV Death**

The analysis will be based on time to the first occurrence of CV death using ITT analysis set. The hazard ratio of canagliflozin compared to placebo and its 95% CI will be estimated using a stratified Cox proportional hazards regression model with treatment as the explanatory variable and history of CV disease (secondary and primary prevention) as the stratification factor. The p-value from the stratified log rank test for the treatment effect will also be reported.

Subgroup analyses will be performed using the same subgroups and the analysis methods described in Section 4.2.2.1.

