### **4.3. Multiplicity Adjustment**

Per the SAP of the integrated summary of CANVAS and CANVAS-R studies, only one alpha family is proposed for the testing of the multiple hypotheses based on the integrated data and the CANVAS-R data. The Type I error for these tests will be strictly controlled via a gatekeeping procedure. If the MACE and the mortality endpoints in the integrated analysis succeed in rejecting the null hypotheses, all of the alpha for testing (ie, 5%) will pass to the CANVAS-R for testing of the primary and the secondary hypotheses of the study. Tests for CANVAS-R hypotheses will proceed sequentially conditional on the statistical significance of the hypothesis tests in the integrated summary at the 5% significant level.

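### Does the superiority rule in SAP 1.4 allow a CANVAS-R claim outside the gatekeeping procedure, and does the 90.5% power mislead by leaving that procedure out?

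*SAP*

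**What the plan says.** SAP 1.4 names the three endpoints, sets a null hazard ratio of at least 1.0 against an alternative below 1.0 for each, and states that the drug "will be claimed to be superior in the reduction of the target events as compared to placebo if the upper bound of 95% CIs" for the hazard ratio lies under 1.0. It does not refer to any other section.

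The multiplicity rule is set out elsewhere. Protocol 11.3.4 says that "testing of the hypotheses in CANVAS-R will not proceed until the hypothesis tests related to the integrated database are significant". SAP 4.3 puts the integrated and the CANVAS-R hypotheses in one alpha family. It sets the precondition, "If the MACE and the mortality endpoints in the integrated analysis succeed in rejecting the null hypotheses", under which the full 5% passes to the study's primary and secondary hypotheses. It then adds: "Tests for CANVAS-R hypotheses will proceed sequentially conditional on the statistical significance of the hypothesis tests in the integrated summary".

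The analysis sections differ in how they refer to this rule. SAP 4.1.2 (primary) applies its Wald test at 0.05 "in the context of multiplicity adjustment described in Section 4.3". SAP 4.2.2.1 and 4.2.2.2 (the two CV endpoints) give a stratified Cox hazard ratio with its interval and add "The p-value from the stratified log rank test for the treatment effect will also be reported", with no threshold and no reference to 4.3. SAP 4 states: "All statistical tests, except those for the primary and secondary efficacy endpoints, will be considered nominal".

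The synopsis promises closed testing at 5% for the primary and secondary endpoints but does not mention the integrated tests. Protocol 11.2 and the synopsis give 90.5% power for albuminuria progression from 693 events, a 22% risk reduction and a two-sided 0.05 level, also without mentioning the integrated tests.

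**The concern.** A claim rule should have one reading. If an integrated MACE or mortality test fails, or an earlier CANVAS-R step fails, SAP 1.4 taken literally still permits a superiority claim that SAP 4.3 rules out. The two CV endpoints look most exposed, because their analysis sections do not point to 4.3 and SAP 1.4 is the only place that states a threshold for them on the hazard ratio scale. SAP 4 exempts the primary and secondary tests from the nominal label without condition, so the visible text does not say how they are labelled when the precondition fails.

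The power figure raises a related worry. A formal claim on albuminuria needs the integrated tests to succeed as well as the primary test, so 90.5% is a ceiling on the chance of that claim. A reader might take it for the chance itself.

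At stake would be an inflated false-claim rate for the study's three hypotheses and an over-optimistic view of the chance of a formal positive result.

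**Working it through.** **1. The plan's own power figure.** Inputs from Protocol 11.2: 693 events, 22% risk reduction read as a hazard ratio of 0.78, two-sided 0.05. Allocation is 1:1 (Protocol 3.1). Schoenfeld's formula:

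power = Φ(√(693/4) × |ln 0.78| − 1.96) = Φ(13.16 × 0.2485 − 1.96) = Φ(1.31) = 0.905.

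This matches the stated 90.5%. The level used is the full 5% that SAP 4.3 passes to CANVAS-R once the integrated tests succeed.

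**2. SAP 1.4 applied with no precondition and no order.** An upper 95% bound below 1.0 is a one-sided 0.025 test. With all three true hazard ratios equal to 1.0, the chance of at least one false claim is:

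- Bonferroni ceiling: 3 × 0.025 = 7.5%.
- Three independent tests: 1 − 0.975³ = 7.3%.
- Albuminuria independent, the two CV tests correlated (bivariate normal, assumed correlations 0.5, 0.8, 0.9): 6.9%, 6.3%, 5.9%.
- CV tests completely correlated: 1 − 0.975² = 4.9%.

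**3. The plan as a whole.** SAP 4.3 tests the three in sequence. To make any false claim, the procedure must reject the first true null hypothesis in the order, and that has probability at most 2.5% in the favourable direction. This holds whatever the order, whatever the correlations, and whichever of the three nulls are true. Requiring the integrated tests to succeed first can only lower it.

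**4. The passages side by side.**

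| Question | Where it is answered |
|---|---|
| What result counts as superiority for one hypothesis? | SAP 1.4 (direction and bound) |
| At what level? | SAP 4.3 (5%, passed on in full); SAP 4.1.2 repeats it for the primary |
| May the hypothesis be tested at all, and when? | SAP 4.3 and Protocol 11.3.4 |
| Are the CV endpoints covered? | Yes: SAP 4.3 names the secondary hypotheses, and Protocol 11.3.4 the key secondary endpoints |

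These answers fit together. If a hypothesis is not reached, no test of it takes place, and the criterion in 1.4 has nothing to act on. For the CV endpoints, an upper 95% bound below 1.0 is essentially the 5% level of SAP 4.3 restated in the favourable direction, so 1.4 adds no separate route to a claim.

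**5. What a power qualifier could say.** Let q be the chance that the integrated tests succeed. Neither document gives q. For any dependence, the chance of a formal primary claim lies between max(0, q + 0.905 − 1) and min(q, 0.905). For illustration only, an assumed q of 0.8 gives 70.5% to 80.0%, and q of 0.5 gives 40.5% to 50.0%. These ranges are driven by the assumed q and say nothing specific about this trial.

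**The case for a change.** The best argument for a change is that the authors saw the need for a link in SAP 4.1.2 and then left it out of 4.2.2.1 and 4.2.2.2, the sections for the endpoints where a claim would attract most attention. The mismatch matters only when the integrated tests or an earlier step fail, which is when a clear rule is most wanted. Repairing it would cost a few words. The handling of results when the precondition fails is also unstated in the visible text.

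Part of this stands. SAP 1.4 has no cross-reference, the analysis sections are uneven, and the synopsis is shorter than Protocol 11.3.4. The further step, that an analyst could therefore make an unprotected claim, does not follow. SAP 4.3 comes directly after 4.2.2.2, names the secondary hypotheses and says that type I error is strictly controlled. Protocol 11.3.4 is equally plain that testing stops. A statistician preparing the report could not use 1.4 without setting both aside.

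On labelling, the testing-sequence figure in SAP 4.3 and the matching display in Protocol 11.3.4 are not reproduced in the copies available, and the integrated SAP to which 4.3 refers is a separate document. Silence in the visible text is weak evidence of a gap. Formal testing is already blocked in that case, so the label is a reporting convention that analysts would fill in as nominal.

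On power, it is ordinary practice to quote the power of the primary test at its own level. Protocol 11.2 ties 90.5% to one endpoint and one level, and SAP 1.1 reports 5,812 subjects already recruited. A qualifier would inform no decision.

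**Conclusion.** No change is called for. The inconsistency is real but clerical: SAP 1.4 gives the criterion for each hypothesis without repeating the condition set in SAP 4.3 and Protocol 11.3.4. Read together, the sections hold the chance of any false superiority claim among the three hypotheses to at most 2.5% in the favourable direction. The 4.9% to 7.3% range describes a reader who applies 1.4 and disregards the other two sections. It rests on assumed correlations and is not an error rate of this plan. The 90.5% power is correct for what it claims to be, and no joint figure can be derived because the chance of passing the integrated tests is not in these documents.

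The conclusion assumes that SAP 4.3 governs when claims are made, as its wording and Protocol 11.3.4 indicate. It does not depend on the order of the CANVAS-R hypotheses, which sits in a figure that is not shown. A cross-reference would be tidier, but it would alter no analysis, error level, sample size or conclusion.

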## **2. GENERAL ANALYSIS DEFINITIONS**

### **2.1. Analysis Populations**

- Randomized subjects—subjects who are randomized via the Interactive Web Response System (IWRS);
- Treated subjects—randomized subjects who received at least one dose of double-blind study medication.

For efficacy analyses and baseline summaries, subjects will be analyzed according to their randomization assignment. For safety analysis (eg, adverse events [AEs]) and summary of exposure, subjects will be analyzed according to the predominant treatment received (defined as the treatment to which the subject was exposed for the greatest duration), in the event that subjects receive a treatment other than the one to which they were randomized. The treatment groups referred in this SAP will be all canagliflozin and placebo.

## 2.2. Analysis Sets

Analysis sets consist of 2 components: 1) analysis population (Section 2.1), which specifies the subjects included in an analysis; 2) data period, defining the time window during which data will be included in the analysis.

**Table 1: Summary of Analysis Sets**

Analysis Set	Analysis Population	Data Period
ITT	Randomized subjects	Day 1 to the last trial contact date (see Section 2.3.2) up to the GTED
On-Study	Treated subjects	Day 1 to the last trial contact date (see Section 2.3.2) up to GTED
On-Treatment	Treated subjects	Day 1 to the last dose date (see Section 2.3.2) plus X a days or the last trial contact date, whichever is earlier.

a X is 2 days for laboratory (except ACR) and vital sign measurements, and 30 days for CV and mortality endpoints, and adverse events (AEs).

## 2.3. Data Handling

### 2.3.1. Censoring Rules

For each analysis set, events that occur any time during the data period of the corresponding analysis set (see Table 1) will be considered as eligible events; otherwise subjects not experiencing an event will be censored at the earlier of the last trial contact day or end of the respective data period, if not otherwise specified.

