Increase dose if subject requires additional glycemic control (see Section 3.1)						X	X		X		
Procedures											
Vital signs, weight, foot examination ^f	X	X				X	X		X	(ask about foot problems and provide foot care guidance)	X
Serum chemistry panel ^g	X	X				X	X		X		X
Hematology ^g		X							Week 52, 104 and 156		X
Fasting serum lipid profile ^g		X					X		Week 52, 104 and 156		X
HbA _{1c}	X	X				X	X		X		X
Duplicate first morning void urines for urine albumin/creatinine (provide collection containers at previous visit) ^{g, h}		X					X		Weeks 52, 78, 104 and 156		X
Urinalysis ^g		X									

Procedures and Evaluations	Pre-treatment		Double-blind treatment						
	Screening ^a	Baseline	Phone/email contact at Week 6	Week 13	Week 26	Phone/email contact at Week 39	Week 52 and thereafter unless otherwise indicated	Phone/email contact midway between 26-week visits until last on-treatment visit	Last on-treatment visit (or after early discontinuation of treatment) ^b
Time point	Week -2	Day 1							
Urine pregnancy test ¹		X							
Dispense glucose testing supplies (optional per country/region)		X		X	X		X		
Ongoing Review									
Concomitant therapy (drug classes of interest) ^j			X	X	X	X	X	X	X
Serious adverse events, and AEs causing discontinuation; vital status; AEs of interest ¹		X	X	X	X	X	X	X	X
CV events		X	X	X	X	X	X	X	X

For footnotes, see below

TIME AND EVENTS SCHEDULE: POSTTREATMENT

Posttreatment

Procedures and Evaluations		Posttreatment Follow-up		
		All Subjects	Subjects Who Withdraw Prior to End of Study	Subjects Who Withdraw Prior to End of Study
Time point		Final visit 30 days after last on-treatment visit (or after early discontinuation of treatment; preferably 30 days after last dose of study drug) ^e	Visit every 26 weeks after last dose until notification of global trial end date (GTED) ^b	Phone/email contact midway between 26 week visits until notification of the GTED ^{b,n}
Procedures				
Vital signs, weight, foot examination ^f			X	X (ask about foot problems and provide foot care guidance)
Serum chemistry panel ^g		X		
Hematology ^g				
Fasting serum lipid profile ^g				
HbA _{1c}				
Duplicate first morning void urines for urine albumin/creatinine (provide collection containers at previous visit) ^{g,i,h}				
Urine pregnancy test ⁱ				
Dispense glucose testing supplies (optional per country/region)				
Ongoing Review				
Concomitant AHA therapy ^j				X

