Subjects are expected to be followed for a maximum of about 3.5 years with the last visit for the last subject targeted to occur when all subjects have approximately 78 weeks of follow-up or when 688 MACE events are accumulated between the CANVAS and CANVAS-R (DIA4003) studies. All sites will be notified of the projected global trial end date (GTED) (projected to occur between January 2017 and April 2017). Immediately after the projected GTED notification is sent, for subjects who remain on double-blind study drug, sites will be required to schedule the last on treatment visits and the 30-day off drug follow-up visits as per the Time and Events schedule; for subjects who prematurely discontinue study drug, sites will be required to make a final contact (eg, schedule the last follow-up visit) or vital status check as soon as possible after announcement of GTED.

All visits (including the 30-day off drug follow-up visit) will need to be completed prior to the GTED.

Figure 5 shows the intended follow-up of randomized subjects with respect to the GTED.

Figure 5: Follow-up of Randomized Subjects with Respect to the GTED

Collection of data about Cardiovascular Safety Outcomes

Investigators will be required to report any cardiovascular (CV) event that they consider could possibly be a nonfatal MI or nonfatal stroke (refer to Section 9.2, Reporting/Adjudication of Events in the CV Composite Endpoint and Other Events for Adjudication), as well as all deaths. Additional information and documentation will be requested from investigators for all such

events to support a detailed assessment of these outcomes by an Endpoint Adjudication Committee.

Collection of Information After Early Discontinuation of Randomized Treatment

It is the intent that subjects who discontinue treatment with the study drug will continue in the study according to the visit schedule described in the Post-treatment Time & Events Schedule. After early discontinuation of randomized treatment, subjects will continue to be followed up for specific data collection, including any MACE events, vital signs, serious adverse events, and adverse events of interest.

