**Figure 3: Hypothesis Testing Sequence**

#### 4.4. Exploratory Efficacy Endpoints

##### 4.4.1. Definition

The following exploratory endpoints will be analyzed:

- Time to the first occurrence of composite endpoint of 40% decrease in eGFR, renal deatha or requirement for renal replacement therapy;
- Time to the first occurrence of composite endpoint of doubling of SCr, renal death or requirement for renal replacement therapy;
- Time to the first occurrence of composite endpoint of 40% decrease in eGFR, renal death, requirement for renal replacement therapy or CV death;
- Time to the first occurrence of composite endpoint of doubling of SCr, renal death, requirement for renal replacement therapy or CV death;
- Time to the first occurrence of composite endpoint of 40% decrease in eGFR, conversion to macroalbuminuria, renal death or requirement for renal replacement therapy;
- Time to the first occurrence of composite endpoint of doubling of SCr, conversion to macroalbuminuria, renal death or requirement for renal replacement therapy;
- Regression of albuminuria;

Regression of albuminuria is the development of normoalbuminuria in a subject with baseline microalbuminuria or macroalbuminuria or the development of microalbuminuria in a subject with baseline macroalbuminuria, accompanied by a decrease in the ACR value of greater than or equal to 30% from baseline. If the ACR at a visit meets the definition of potential regression described above, a confirmatory ACR collection approximately 1 to 2 months later

a Non-CV death with a renal proximate cause is considered as renal death.

(or sooner under unusual circumstances, eg, subject is stopping study drug), should be done. In cases where a confirmatory sample is not collected within 1 to 2 months, the next available set of ACR measurements can be used for confirmation.

- Change in urinary ACR over time;
- Change in eGFR from baseline to the last off-drug measurement;
- Estimated eGFR slopes using all on-drug measurements;
- Changes in HbA1c.
- AHA utilization

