#### **4.4.2. Analysis Methods**

##### **4.4.2.1. Renal Endpoints**

###### **4.4.2.1.1. Composite Endpoints**

The components of the renal composite endpoints, such as requirement for renal replacement therapy and doubling of serum creatinine, identified by the investigator or the sponsor for meeting the criteria pre-specified in the charter will be sent to the independent EAC.

The time to the first occurrence of each of the renal composite endpoints (see Section 4.4.1) will be analyzed in the ITT analysis set using a Cox proportional hazards model with treatment and baseline eGFR ( $< 60$ ,  $\geq 60$  mL/min/1.73m^2) as the explanatory variables. The hazard ratio of canagliflozin compared to placebo and its 95% confidence interval will be estimated from the model.

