###### **4.4.2.1.2. Regression of Albuminuria**

Regression of albuminuria will be analyzed in a similar fashion in modeling and censoring rule as the analysis for progression of albuminuria. The analysis will be using the ITT analysis set based on ACR measurements from a single visit whether confirmed or unconfirmed. Subjects with normal albuminuria at baseline will be excluded. The hazard ratio of canagliflozin compared to placebo and its 95% confidence interval will be estimated from the model. Additionally, analyses based on confirmed regression plus unconfirmed regression from the last ACR values will be performed in a similar fashion using ITT analysis set.

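### The six exploratory renal composites keep early stoppers at risk to last contact, but after the early-withdrawal and 30-day visits no scheduled test can show a laboratory event

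*SAP*

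**What the plan says.** **Endpoints.** SAP 4.4.1 lists six renal composites. All contain either a 40% fall in eGFR or a doubling of serum creatinine. Two also contain an ACR component, for example "Time to the first occurrence of composite endpoint of 40% decrease in eGFR, conversion to macroalbuminuria, renal death or requirement for renal replacement therapy".

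**Analysis.** SAP 4.4.2.1.1 says that each composite "will be analyzed in the ITT analysis set using a Cox proportional hazards model with treatment and baseline eGFR" category as explanatory variables. It does not mention censoring.

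**Default censoring.** SAP 2.3.1 applies unless something else is specified: "subjects not experiencing an event will be censored at the earlier of the last trial contact day or end of the respective data period". Under SAP 2.3.2 the last contact can be a telephone visit or a third party confirming survival.

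**Pure ACR endpoints.** Event-free subjects in the progression analysis (SAP 4.1.2) are handled differently: "subjects will be censored at the last ACR measurement up to GTED". SAP 4.4.2.1.2 carries this over: "Regression of albuminuria will be analyzed in a similar fashion in modeling and censoring rule as the analysis for progression of albuminuria".

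**Testing after stopping.** The Protocol's Time and Events Schedule marks chemistry and ACR at the last on-treatment or early-discontinuation visit. The posttreatment schedule marks chemistry in one column only: "Final visit 30 days after last on-treatment visit (or after early discontinuation of treatment; preferably 30 days after last dose of study drug". ACR is marked in none of its columns, and the 26-week visits and telephone contacts carry no renal laboratory test. Protocol 3.1 describes follow-up after stopping as "including any MACE events, vital signs, serious adverse events, and adverse events of interest".

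**The concern.** A subject who stops early and is then followed by visits and calls contributes time at risk for an eGFR fall, a creatinine doubling or macroalbuminuria until last contact. Scheduled measurement of these ended up to years before. The laboratory event rate is diluted in both arms, and more in the arm that stops more. If stopping differs by arm, the renal hazard ratios move for a reason unrelated to the kidney, and a single last-contact analysis cannot show that this has happened.

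Deaths and renal replacement can still be learned of at later contacts, so last contact suits those components. The mismatch is confined to the laboratory components.

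**Working it through.** **Inputs (Protocol 11.2).** N = 5,700, 1:1; placebo progression 7.4% per year; 22% reduction (HR 0.78); 18-month accrual and 36-month maximum, so follow-up F is uniform on 1.5–3.0 years (mean 2.25); treatment discontinuation 10% per year, read as hazard d = 0.10 or d = −ln 0.9 = 0.1054.

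**1. The plan's own figures.**
- Power at 693 events: √693/2 × |ln 0.78| − 1.96 = 3.27 − 1.96 = 1.31, giving 90.5%, as stated.
- Expected events per arm: 2,850 × h/(h+d) × [1 − mean of e^(−(h+d)F)]. If ACR observation ends at stopping: 390.3 + 309.9 = 700.2 (d = 0.10), or 388.1 + 308.1 = 696.2 (d = 0.1054). With full follow-up: 435.9 + 346.3 = 782.2.
- The stated 693 fits the first reading. The plan's own event count thus behaves as if ACR observation ends with study drug.

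**2. Person-time no scheduled test covers.** Let g be the time from stopping to the last scheduled test: 0 for ACR, 30/365.25 = 0.082 years for creatinine. Mean covered time = g + [1 − mean of e^(−d(F−g))]/d.
- Creatinine, d = 0.10: 0.082 + 0.1941/0.10 = 2.024 years; 1 − 2.024/2.25 = **10.1%**. With d = 0.1054: 2.012 years, **10.6%**.
- ACR: 2.007 and 1.995 years, **10.8%** and **11.3%**.
- Subjects who stop more than 30 days before their follow-up ends: 19–20%.

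Of 5,700 × 2.25 = 12,825 person-years, about 1,290–1,350 lie beyond the last scheduled creatinine.

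**3. Effect on the laboratory hazard ratio.** For uncommon events, last-contact censoring multiplies each arm's laboratory rate by roughly its covered share c. The covered shares at 8, 9, 11 and 12% per year are 0.918, 0.909, 0.890 and 0.881. The ratio moves by c(canagliflozin)/c(placebo):

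| Stopping per year, placebo / canagliflozin (unequal splits assumed) | Shift by this formula | Simulated Cox shift |
|---|---|---|
| 10 / 10% | 0 | −0.03 to +0.1% |
| 11 / 9% | 0.909/0.890: +2.1% | +2.1 to +2.2% |
| 12 / 8% | 0.918/0.881: +4.2% | +4.2 to +4.7% |
| 8 / 12% | 0.881/0.918: −4.0% | −3.9 to −4.1% |

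The simulations assumed laboratory hazards of 2% or 5% per year and a true HR of 0.70.

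**4. Effect on a composite.** If half the events are non-laboratory and always seen, with the same HR, the 12/8% shift is (1 + 0.918)/(1 + 0.881) = 1.020, or about +2%. The 8/12% shift is about −2%. If half of the later laboratory events are found anyway, the laboratory shift also falls to about 2%.

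**5. Does the remedy work?** Assume laboratory hazard 2% (HR 0.70) and death hazard 2% (HR 0.80), so the true composite HR is (0.014 + 0.016)/0.040 = 0.75. Over equal, 12/8% and 8/12% stopping, simulated HRs were 0.731–0.766 with last-contact censoring and 0.746–0.755 when early stoppers' follow-up ended 30 days after the last dose. Censoring the whole composite at the last creatinine gave about 0.70 even with equal stopping, because every death follows the subject's last creatinine and is lost.

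**The case against.** **The two rules need not conflict.** A reader might infer that the SAP contradicts itself. It does not: progression and regression are pure ACR endpoints, while the composites include deaths and renal replacement that remain observable. Last contact is a defensible main rule. What is missing is an analysis that shows how much it matters.

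**Testing does not cease on the day of stopping.** The early-withdrawal evaluation takes chemistry and ACR, a repeat ACR may follow, and SAP 4.1.4.3 refers to some post-treatment ACR data. Components "identified by the investigator or the sponsor for meeting the criteria pre-specified in the charter will be sent to the independent EAC", so unscheduled detection is possible, and subjects may restart drug. These shrink the gap but do not close it. The charter that governs referral is not available here.

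**The effect is small and conditional.** This stands. Under the assumptions above there would be about 190 or 470 laboratory events, with a standard error of ln HR near 2/√190 = 0.14 or 2/√470 = 0.09. The 12/8% shift is then about 0.3–0.5 of a standard error.

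**Stronger readings that the documents do not support.**
- That the renal results favour one arm: the direction depends on which arm stops more, and the documents do not say.
- That CV death or heart-failure hospitalization has a comparable defect: CV events and serious adverse events are collected at posttreatment contacts. With an assumed 5–25% of stoppers having a survival-only last contact, the HR moves by only 0.1–0.6%.
- That the primary analysis needs the same repair: it already censors at last ACR, and SAP 4.1.4.3 plans a copy-control imputation for early stoppers.

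**Conclusion.** The point holds for the laboratory components of the six exploratory renal composites. At the plan's stopping rate, about 10–11% of person-time at risk lies beyond the last scheduled test, so laboratory event rates are understated by about that share. The laboratory hazard ratio is unaffected by equal stopping. It shifts by about 2% at 11% versus 9% per year and 4–5% at 12% versus 8%; a half-laboratory composite shifts by about half as much. The unequal splits, component hazards and hazard ratios are assumptions, and so is the premise that stoppers are followed by contact to the end. Type I error, the primary endpoint and the secondary endpoints are not in question. This is an inexpensive improvement to how exploratory results can be read, best fixed before unblinding so that the censoring date is not chosen with results in view.

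**What to change.** Keep the last-contact analyses and add to SAP 4.4.2.1.1:

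- **(a)** An analysis of the laboratory components alone (40% eGFR decrease; doubling of serum creatinine; conversion to macroalbuminuria), with event-free subjects censored at the last creatinine or last ACR, as applicable.
- **(b)** For each composite, a sensitivity analysis that ends follow-up for early stoppers at the 30-day off-drug visit (last dose plus 30 days, with the protocol's ±12-day window) and counts deaths and renal replacement up to that date as events. The On-Treatment set in SAP Table 1 cannot simply be reused, because its 2-day laboratory window would drop the 30-day creatinine.
- **(c)** Stopping by arm shown beside (a) and (b). SAP 3.3 already plans that summary.

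State that the whole composite is not to be censored at the last creatinine. State also that (b) assumes stopping is unrelated to later renal risk, which is why it stands beside the main analysis and does not replace it.

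Cost: a few SAP sentences, derived censoring dates and a few extra runs; about 10% less follow-up and slightly fewer events in (b). No new data, protocol amendment or change to the alpha-controlled tests is needed.
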